## 7.9. Reader Reliability

There are four imaging readers who were trained to perform our central reads used in much of the analyses. Only three of these readers will perform these reads with the fourth reader as an alternative if needed. Variability of these readers regarding the primary endpoint for the evaluable set will be tested as described below. The following is assumed:

Ni=total number of subjects with the primary endpoint in the evaluable set (i=1, 2,...N)

K=number of readers (3)

 $R_i$ = number of responses (i=1,2)

nij=number of times subject i is in response group j

#### 7.9.1. Intra-Reader Reliability

Prior to reading any images, a random subset of 30 PyL images will be randomly selected by the Imaging vendor. Once the reads start, this subset will be re-introduced to each reader no sooner than 3 weeks after the original read. They will be read under identical conditions as the original read (same criteria evaluation, same analysis reporting, same analysis platform). The rate of agreement between the original reads and the re-reads for the primary endpoint in this subset will be compared using the intra-rater variability defined from Cohen's Kappa. This calculation will be performed for each reader separately.

Cohen's Kappa = 
$$\frac{p_{a-}p_e}{(1-p_e)}$$
where  $p_a = \sum_{j=1}^R \frac{n_{jj}}{n}$ 

$$p_e = \sum_{j=1}^R \frac{n_{j+}}{n} \frac{n_{+j}}{n}$$

The standard error of Kappa  $\sigma_k\,\underline{w}ill$  be calculated as:

$$\sigma_{k} = \sqrt{\frac{P_{a}(1-P_{a})}{N(1-P_{e})^{2}}}$$

It is assumed that the concordance rate between time points for each reader will be at minimum of 93% with a Kappa of 86%. This would yield a 95% confidence interval of (0.68, 1) for a sample of 30 subjects.

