#### 7. EFFICACY

#### 7.1. General Considerations

Statistical tests and their corresponding confidence intervals will be two-sided at the 0.05 significance level.

The estimation of sensitivity and specificity rely on the central imaging core lab independent readers. Each reader's assessments will be summarized separately.

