## 7.2. Testing Statistical Assumptions Including Comparability at Baseline

#### 7.2.1. Test of Proportions

The assumption underlying the normal approximation to the binomial distribution, used in the computation of confidence intervals for sensitivity, specificity, PPV, and NPV, is that the sample size is such that np>5 and n(1-p)>5, where n is the sample size and p is the binomial probability. It is expected that the sample size for each statistic will be sufficient to meet this assumption. In the event that the sample size is not sufficient, Agresti-Coull exact tests will be used. As there is only one treatment in this study, there will be no testing of baseline comparability.

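### The normal-theory interval implied for intra-reader kappa collapses to (1, 1) when a reader repeats all 30 calls, and covers about 88% rather than 95% at the SAP's minimum agreement

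*SAP*

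**What the plan says.** SAP 7.9.1 (Intra-Reader Reliability) assesses whether each central reader repeats his or her own primary-endpoint call. Before reading starts, "a random subset of 30 PyL images will be randomly selected by the Imaging vendor". Those images return to each reader at least three weeks after the first read, and agreement is summarised by Cohen's kappa. "This calculation will be performed for each reader separately".

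The section defines kappa as (Pa − Pe)/(1 − Pe), with Pa the observed and Pe the chance agreement. It gives the standard error as sqrt(Pa(1 − Pa) / (N(1 − Pe)²)). The planning statement is "It is assumed that the concordance rate between time points for each reader will be at minimum of 93% with a Kappa of 86" per cent, followed by "This would yield a 95% confidence interval of (0.68, 1) for a sample of 30 subjects".

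Two other sections bear on this. SAP 7.1 sets the level: "Statistical tests and their corresponding confidence intervals will be two-sided at the 0.05 significance level". SAP 7.2.1 accepts the normal approximation for sensitivity, specificity, PPV and NPV provided that "the sample size is such that np>5 and n(1-p)>5", and otherwise turns to Agresti-Coull. It does not mention kappa, and 7.9.1 has no fallback of its own.

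**The concern.** The formula is a normal approximation applied to a proportion that the plan expects to be close to 1, with only 30 observations. Two symptoms are visible without any simulation. The upper limit of the SAP's own example exceeds 1 before it is cut. And the standard error contains the factor Pa(1 − Pa), so it is zero when a reader agrees with himself or herself on every scan. A 95% interval of zero width from 30 scans would claim certainty that the data cannot give.

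The 93% figure is stated as a minimum, so the plan expects readers at or above it, and that is where the approximation is worst. At stake is the precision attached to each reader's repeatability. This is supporting evidence for reads on which the co-primary result rests reader by reader, but it is not the co-primary result itself.

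**Working it through.** **Inputs.** N = 30 re-reads, Pa = 0.93, kappa = 0.86 and the standard error formula (SAP 7.9.1); two-sided 95%, so z = 1.96 (SAP 7.1). Agreement of 95% or 97%, and positive-read rates of 10% to 50%, are assumptions used to show a range. SAP 4.3 gives only a 20% probability of positive histopathology.

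**1. Reproduce the SAP's figure.**
- Implied chance agreement: Pe = (0.93 − 0.86)/(1 − 0.86) = 0.50.
- SE = sqrt(0.93 × 0.07 / 30) / 0.50 = 0.0932.
- 0.86 ± 1.96 × 0.0932 = (0.677, 1.043), which is (0.68, 1) after cutting at 1.

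The printed interval is therefore arithmetically correct and identifies the method: kappa ± 1.96 SE with N = 30.

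**2. Zero standard error.** If all 30 pairs agree, Pa = 1, SE = 0 and the interval is (1, 1). The probability is Pa^30, and such an interval misses any true kappa below 1, so coverage cannot exceed 1 − Pa^30. This ceiling does not depend on the positive-read rate or on the direction of disagreements.

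**3. Exact coverage.** All possible 2×2 tables (original read by re-read) were enumerated for N = 30, with independent images, equal marginals and Pe re-estimated in each table. At a 50% positive-read rate (Pe = 0.50):

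| True agreement | P(all 30 agree) | Ceiling | Exact coverage |
|---|---|---|---|
| 93% (SAP minimum) | 0.113 | 88.7% | 88.3% |
| 95% (assumed) | 0.215 | 78.5% | 78.2% |
| 97% (assumed) | 0.401 | 59.9% | 59.7% |

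At a 20% positive-read rate the coverages are 87.8%, 78.3% and 59.8%, so the result barely depends on Pe.

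**4. Direction of the misses.** At 93% agreement and Pe = 0.50, the interval lies wholly above the true kappa in 11.3% of cases and wholly below it in 0.4%.

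**5. The SAP's own small-sample check.** n(1 − p) = 30 × 0.07 = 2.1, which would fail the requirement of more than 5 in 7.2.1 if that check applied to agreement.

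**6. Alternative limits.** Compute limits for Pa and convert each by (p − Pe)/(1 − Pe). With 30 of 30 agreeing and Pe = 0.50:
- Wilson: lower limit for Pa = 30/(30 + 3.84) = 0.886, so kappa is (0.77, 1).
- Agresti-Coull: adjusted n = 33.84; adjusted p = (30 + 1.92)/33.84 = 0.943; lower limit = 0.943 − 1.96 × sqrt(0.943 × 0.057/33.84) = 0.865, so kappa is (0.73, 1).

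Exact coverage by the same enumeration, at 93% to 97% agreement:

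| Positive-read rate | Wilson | Agresti-Coull |
|---|---|---|
| 20% to 50% | about 94% to 96% | about 96% to 99% |
| 10%, lowest value | about 90% | about 95% |

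Undefined kappa (every read the same at both times) is counted as a miss.

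**The case against.** The strongest objection is importance. Intra-reader kappa is not a primary, secondary or exploratory endpoint, it has no hypothesis or threshold, and its table (14.2.3-14) is listed under exploratory efficacy. A reader might infer that the co-primary conclusion is at risk. The documents do not support that: the tests in SAP 7.6.1 do not use kappa. Nor are the kappa and agreement estimates biased by this formula; only the interval is wrong. This objection stands and sets the priority.

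Second, 7.9.1 does not expressly promise a confidence interval, whereas 7.9.2 does for the inter-reader kappa. That the interval will be reported this way is an inference from the standard error and the worked example. It is a strong inference, because the example reproduces in no other evident way.

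Third, failing the n(1 − p) > 5 check might be read as the SAP breaking its own rule. It is not: 7.2.1 covers four named statistics, and kappa is not one of them. The comparison shows a gap, not a contradiction.

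Fourth, SAP 7.9 defines its sample size as the "total number of subjects with the primary endpoint in the evaluable set", and a reader might infer that the kappa standard error would be computed with some 236 subjects and so be far too small. The text rules this out. Section 7.9.1 confines the calculation to the re-read subset and states its example for 30 subjects.

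Fifth, one might multiply the 11% over three readers to get the chance that at least one shows (1, 1). That needs independence between readers, and all of them re-read the same images, so no such figure is given here.

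Finally, 95% and 97% agreement are assumed scenarios. Only the 93% result rests on the SAP's stated value.

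**Conclusion.** The concern holds for the interval. As implied by SAP 7.9.1, the nominal 95% interval for intra-reader kappa covers about 88% at the SAP's minimum agreement, and about 78% or 60% if agreement is really 95% or 97%. Each reader who truly agrees 93% of the time has an 11% chance of a zero-width interval at 1. The errors run almost entirely in the favourable direction, since the lower limit is too high.

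The coverage figures assume 30 usable and independent image pairs and symmetric disagreement; the ceiling from the zero standard error needs only the first two. If fewer than 30 images yield a primary-endpoint result, the ceiling at 93% agreement is lower: with 25 pairs it is 1 − 0.93^25 = 83.7%. The printed example is correct arithmetic and no trial conclusion depends on this interval. Priority is low to moderate.

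**What to change.** In SAP 7.9.1, keep the kappa estimate and replace the interval. Compute 95% limits for Pa by Agresti-Coull, cut at 1, or by Wilson, and convert each limit by (p − Pe)/(1 − Pe). Agresti-Coull has the advantage that the SAP already names it as its fallback, and it held about 95% or more in every setting examined. Wilson is narrower and closer to nominal at 20% to 50% positive reads, but can fall to about 90% when positive reads are rare. Both treat the estimated Pe as known, which is why coverage weakens at low positive rates.

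Add one rule: if Pe = 1, report kappa as not estimable and give raw agreement with its interval.

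The cost is about two sentences in the SAP and a few lines of code, with no new data and no change in design. The drawback is a wider, less favourable interval at high agreement: about (0.73, 1) or (0.77, 1) instead of (1, 1) for 30 of 30 at Pe = 0.50.

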## 4.3. Sample Size

The primary analysis in Cohort A will test the co-primary endpoints of sensitivity and specificity of F-DCFPyL PET imaging relative to histopathology for the evaluable set of subjects in Cohort A with metastatic disease. For each co-primary endpoint, there will be three independent imaging readers. At least two of the three readers must reject the null hypothesis for specificity to be deemed a success. If specificity is a success, then the same two readers need to reject the null hypothesis for sensitivity leading to overall success of the primary endpoint. The null hypotheses will be tested in the following order:

- 1. Specificity of F-DCFPyL PET imaging relative to histopathology in Cohort A  $H_0$ :  $\pi_{Sp} = 0.80$  versus  $H_1$ :  $\pi_{Sp} \neq 0.80$
- 2. Sensitivity of F-DCFPyL PET/CT imaging relative to histopathology in Cohort A  $H_{01}$ :  $\pi_{Se} = 0.40$  versus  $H_{11}$ :  $\pi_{Se} \neq 0.40$

where  $\pi_{Se}$  is the true sensitivity and  $\pi_{Sp}$  is the true specificity of F-DCFPyL PET imaging.

A total of 262 subjects from Cohort A will provide 80% power to reject the null hypothesis about sensitivity at the 5% significance level if the true sensitivity is at least 60% and at least 80% power to reject the null hypothesis about specificity at the 5% significance level if the true specificity is at least 87.8%. These calculations are based on the following assumptions:

• the probability of a positive histopathology sample in Cohort A is 20%,

The sample size is based on the normal approximation to the binomial distribution without a continuity correction.

$$n \ge \left\{ \frac{z_{\alpha/2} \sqrt{P_0(1 - P_0)} + z_{\beta} \sqrt{P_1(1 - P_1)}}{P_1 - P_0} \right\}^2$$

where P0 are P1 are values of sensitivity under the null and alternative hypotheses, respectively. After adjusting sensitivity and specificity separately by their corresponding prevalence values, a total in 236 subjects are needed. Assuming a 10% drop out or non-evaluable rate increases the required number of subjects in Cohort A to 262.

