14.2.3-10	PPV and Positive Imaging from any tissue compared to histology for both Cohorts Combined -Change in Management Set		
14.2.3-11	Summary of Imaging Results-Safety Set		
14.2.3-12	Summary of Histology Results- Safety Set		
14.2.3-13	Summary of Procedures- Safety Set		
14.2.3-14	Inter-Reader and Intra-Reader Variability for Cohort A- Evaluable Set		
14.2.4: Ef	14.2.4: Efficacy- Per Protocol Set		
14.2.4-1	Specificity and Sensitivity of the Pelvic Lymph Nodes for the Subjects in Cohort A- Per-Protocol Set		
14.3.1: Ad	lverse Events- Safety Set		
14.3.1-1	Summary of Treatment Emergent Adverse Events, Overall and by Cohort -Safety Set		
14.3.1-2	Most Frequent (>5% Overall) Treatment Emergent Adverse Events, Overall and by Cohort-Safety Set		
14.3.1-3	Treatment Emergent Adverse Events Overall and by Cohort- Safety Set		
14.3.1-4	Serious Treatment Emergent Adverse Events Overall and by Cohort- Safety Set		
14.3.1-5	Drug Related Treatment Emergent Adverse Events Overall and by Cohort- Safety Set		
14.3.1-6	Treatment Emergent Adverse Events where Severity Grade>=3, Overall and by Cohort-Safety Set		
14.3.1-7	Treatment Emergent Adverse Events by Severity Grade, Overall – Safety Set		

14.3.2: Lis	sting of Deaths and Other Serious and Significant Adverse Events- Safety Set
14.3.1-1	Listing of Treatment Emergent Adverse Event Leading to Discontinuation or Death- Safety Set
14.3.1-2	Listing of Treatment Emergent Adverse Events Deemed Serious or With a Grade 3 or Above- Safety Set
14.3.4: Ab	onormal Laboratory Value Listing
14.3.4-1	Listing of Abnormal Hematology Results – Safety Set
14.3.4-2	Listing of Abnormal Chemistry Results- Safety Set
14.3.5: Vi	tal Signs
14.3.5-1	Summary and Change from Baseline in Vital Signs- Safety Set
14.3.6: Ot	her Safety Data
14.3.6-1	Summary and Change from Baseline in Hematology Results- Safety Set
14.3.6-2	Summary and Change from Baseline in Chemistry Results- Safety Set
14.3.6-3	Clinical Laboratory Shift Table: Chemistry- Safety Set
14.3.6-4	Clinical Laboratory Shift Table: Hematology- Safety Set
14.3.6-5	Summary and Change from Baseline in ECG Parameters- Safety Set
14.3.6-6	Concomitant Medications- Safety Set
14.3.6-7	Study Drug Exposure- Safety Set
14.4: PK I	Evaluations
14.4-1	Percent of Dose Recovered in Urine per Collection Interval -PK Urine Set
14.4-2	Summary of Urinary Kinetics- PK Urine Set
Listings	
16.2.1-1	Listing of Discontinuations – Consented Population
16.2.2-1	Listing of Protocol Deviations – Safety Set

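### The planned intra-reader kappa interval of (0.68, 1) needs about half of reads to be positive and 30 subjects with the primary endpoint; SAP 4.3 implies about 22% positive, and the sampling frame is not stated

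*SAP*

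**What the plan says.** SAP 7.9.1 sets up the re-reads as follows: "Prior to reading any images, a random subset of 30 PyL images will be randomly selected by the Imaging vendor". The quantity assessed is "The rate of agreement between the original reads and the re-reads for the primary endpoint in this subset", summarised by Cohen's kappa separately for each reader. The planning statement is "It is assumed that the concordance rate between time points for each reader will be at minimum of 93% with a Kappa of 86" (both figures are percentages), followed by "This would yield a 95% confidence interval of (0.68, 1) for a sample of 30 subjects".

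Four other places bear on it:

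- The opening of SAP 7.9 fixes the variable and the set: "Variability of these readers regarding the primary endpoint for the evaluable set will be tested as described below".
- SAP 5.5.7.1 defines the primary endpoint for Cohort A subjects only, and requires a lymphadenectomy before an imaging result can be counted as negative.
- SAP Table 4 lists the output as "Inter-Reader and Intra-Reader Variability for Cohort A- Evaluable Set".
- SAP 4.3 assumes that "the probability of a positive histopathology sample in Cohort A is 20" per cent. It states power at sensitivity 60% and specificity 87.8%, against null values of 40% and 80%, and allows 10% for dropout or non-evaluability (236 evaluable of 262).

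Protocol 6.2 plans about 262 dosed subjects in Cohort A and 115 in Cohort B.

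**The concern.** Kappa depends on chance agreement, which depends on how often readers call a scan positive. An assumed concordance and an assumed kappa together fix the chance agreement, so the SAP has in effect assumed a positive rate without naming it. That rate should match the one implied by the sample-size section, and it does not.

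The standard error also uses N = 30. Only a subject with the Cohort A primary endpoint can contribute to this kappa, and the text selecting the 30 images mentions neither cohort nor evaluability.

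This is the only precision the plan states for intra-reader repeatability, and the success rule works reader by reader. If the planning figure is too favourable, the re-read exercise will be less informative than intended. An observed kappa near 0.79 at 93% agreement could also be misread as falling short of plan, when it is what 93% agreement gives at the expected positive rate.

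**Working it through.** **Formulas (SAP 7.9.1).** Pa is observed agreement and Pe is chance agreement.

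- kappa = (Pa − Pe)/(1 − Pe)
- SE = √[Pa(1 − Pa)/(N(1 − Pe)²)]
- 95% interval = kappa ± 1.96 × SE, cut off at 1

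**Step 1: reproduce the SAP's interval.** With Pa = 0.93 and kappa = 0.86:

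- Pe = (0.93 − 0.86)/(1 − 0.86) = 0.50
- SE = √[0.93 × 0.07/(30 × 0.25)] = 0.0932
- Interval = 0.86 ± 0.183 = (0.677, 1.043), reported as (0.68, 1)

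If both reads have the same positive rate q, then Pe = q² + (1 − q)², and Pe = 0.50 means q = 50%. Allowing for rounding in 93%, 86% and 0.68, q could be as low as about 38%, but no lower.

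**Step 2: positive rate implied by SAP 4.3.**

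- q = prevalence × sensitivity + (1 − prevalence) × (1 − specificity) = 0.20 × 0.60 + 0.80 × 0.122 = 0.2176
- Pe = 0.2176² + 0.7824² = 0.6595

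At 20% prevalence and 60% sensitivity, a 50% positive rate would need a false-positive rate of (0.50 − 0.12)/0.80 = 47.5%. The SAP's specificity assumption corresponds to 12.2%.

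**Step 3: interval at that rate, N = 30.**

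- Concordance held at 93%: kappa = (0.93 − 0.6595)/0.3405 = 0.794, SE = 0.137, interval (0.53, 1).
- Kappa held at 0.86: Pa = 0.86 × 0.3405 + 0.6595 = 0.952, SE = 0.114, interval (0.64, 1).

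**Step 4: other accuracy values (prevalence 20%, concordance 93%, N = 30).**

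| Sensitivity | Specificity | q | Pe | kappa | Lower limit |
|---|---|---|---|---|---|
| 60% | 87.8% | 21.8% | 0.660 | 0.79 | 0.53 |
| 40% | 80% (null values) | 24.0% | 0.635 | 0.81 | 0.56 |
| 100% | 87.8% | 29.8% | 0.582 | 0.83 | 0.61 |
| 60% | 100% | 12.0% | 0.789 | 0.67 | 0.24 |

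**Step 5: usable number.**

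- Draw from Cohort A only, 10% non-evaluable: 30 × 236/262 = 27.0
- Draw across both cohorts, all Cohort A subjects: 30 × 262/377 = 20.8
- Draw across both cohorts, evaluable Cohort A subjects: 30 × 236/377 = 18.8

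| Usable N | Lower limit, Pe = 0.50 (kappa 0.86) | Lower limit, Pe = 0.66 (kappa 0.79) |
|---|---|---|
| 30 | 0.68 | 0.53 |
| 27 | 0.67 | 0.51 |
| 21 | 0.64 | 0.47 |
| 19 | 0.63 | 0.46 |

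Both columns hold concordance at 93%. The positive rate matters more: alone it moves the limit from 0.68 to 0.53, while the usable number alone moves it only to between 0.63 and 0.67.

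**Step 6: what the SAP's half-width would cost.** To keep 0.183 at q = 21.8% and 93% concordance, N = [0.93 × 0.07/0.3405²] × (1.96/0.1826)², or about 65 re-reads.

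**The case against.** **The interval is correct for its inputs.** This stands. A reader might infer a calculation error from the different result at 22% positive. There is none; the SAP's formula and inputs give its interval. The fault is an unstated chance agreement that conflicts with SAP 4.3.

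**93% is a floor.** This stands in part. The SAP gives it as a minimum, so a higher concordance that keeps kappa at 0.86 is compatible with the text. The lower limit is then 0.64, a shift of 0.04 rather than 0.15. Treating 0.53 as the only correct replacement would therefore be too strong. But neither reading recovers 0.68 with 30 subjects.

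**22% is not a forecast.** This is fair. The sensitivity and specificity in SAP 4.3 are power alternatives, worded as minimum values. The null values or perfect sensitivity soften the result, to 0.56 and 0.61. Higher specificity worsens it. None of the cases in Step 4 comes near 50% positive.

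**The draw may already be confined to Cohort A.** A reader might infer from the reference to PyL images in general that both cohorts are sampled and about a third of the re-reads are lost. The SAP does not say so. The surrounding text and the title of the output table point towards Cohort A, and the Imaging Manual and Imaging Review Charter cited in protocol 10.2 were not available and may settle it. What can be said is that the SAP states no frame. Because selection precedes any read and carries no evaluability condition, nothing in it secures 30 usable subjects. The 0.46 to 0.47 limits apply only if both cohorts are drawn.

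**Little depends on it.** This is correct. No acceptance threshold or test uses the planning interval, and the reported kappa and standard error will use observed agreement and observed chance agreement.

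**Conclusion.** Wrong as written with respect to the stated precision, and minor.

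On the SAP 4.3 planning values, 30 usable subjects give about (0.53, 1) with kappa 0.79 at 93% concordance, or about (0.64, 1) if kappa 0.86 is kept through 95.2% concordance. The first becomes about (0.51, 1) if 30 Cohort A images leave 27 evaluable.

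This rests on three assumptions: the same positive rate at both reads, the SAP's own large-sample standard error, and a re-read subset that resembles Cohort A as planned. The sampling frame is a gap in specification, not a demonstrated loss of subjects.

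A reader might also infer that a less precise kappa weakens the primary result. The documents do not support that: the primary analysis in SAP 7.6.1 tests specificity and sensitivity for each reader and makes no use of the re-read kappa.

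**What to change.** 1. State in SAP 7.9.1 that the re-read images are drawn from Cohort A, and say how subjects who prove non-evaluable are handled. If 30 usable subjects are wanted, draw about 34 (30 ÷ 236/262 = 33.3). If the draw has already been made, state its frame and the usable number.
2. Restate the planning figure at the expected positive rate and usable number: kappa about 0.79 with an interval of about (0.51, 1) at N = 27, or (0.53, 1) at N = 30. Show the range over concordance and positive rate beside it.
3. If a half-width of about 0.18 was the real target, say so and plan about 65 re-reads; otherwise accept the wider interval.

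The first two cost an instruction to the imaging vendor, a few extra re-reads at most, and one less favourable figure in the SAP. Only the third would add substantial reading work, and it is optional.
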